STUDY PROPOSAL

**Intraoperative Ketamine and Methadone for
Laminectomy: Effect on Recovery, Postoperative Pain,
and Opioid Requirements**

IRB #: Pro00030109

NCT02252432

Date: 02/15/2020

**Intraoperative Ketamine and Methadone for Laminectomy: Effect on Recovery,
Postoperative Pain, and Opioid Requirements**

IRB #: Pro00030109

PRINCIPAL INVESTIGATOR

[name]., Ph.D.

CO-INVESTIGATORS

[name] [name].

INSTITUTION

Department of Anesthesiology
Cedars-Sinai Medical Center
[name]
[name]

E-MAIL

[contact]

[contact]

[contact]

STUDY OBJECTIVES

1. To determine if intraoperative double NMDA antagonism with ketamine + methadone reduces postoperative pain scores and opioid consumption more than single NMDA antagonism with ketamine or methadone alone after lumbar laminectomy.
2. To compare the side effects and hospital course between post-laminectomy patients receiving intraoperative ketamine + methadone vs. ketamine or methadone alone.

BACKGROUND & SIGNIFICANCE

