2. Methadone group: Will receive a single dose of IV methadone (0.2 mg/kg) preinduction.
3. Ketamine + methadone group: Will receive methadone (0.2 mg/kg) preinduction, a bolus of IV ketamine (0.5 mg/kg) during induction and and IV ketamine infusion intraoperatively (5 mcg/kg/min)

Perioperative anesthetic management will be standardized as well as post-anesthesia care unit (PACU) IV opioid administration, which will be based on verbal-rating scale (VRS) pain scores. Patients will be discharged from the PACU and sent to the floor. They will be placed on a pain medication regimen that often includes oral and IV narcotics as needed (PRN). Opiate consumption, VRS pain scores, and adverse events will be recorded on post-operative days one to three and at six weeks.

METHODS

I. Recruitment

- a. Study investigators will contact surgeons who routinely perform lumbar spine surgery and present the study protocol to the surgeons. During the preoperative visit (3 to 15 days prior to surgery), the surgeons and/or assistants will hand the study material packet to potential subjects. Those interested in participating will sign the initial patient contact letter, which includes their phone number and e-mail address.
- b. Study investigators will call these patients, explain the study protocol including the potential risks, benefits, and alternatives and address any questions/concerns. In this manner, potential subjects will have more than 24 hours to decide on signing the consent document.
- c. Only patients providing written consent and indicated that they have been introduced to the study prior to meeting with the anesthesiologists on the day of surgery will be able to participate and undergo screening.
- d. Screening procedures (see inclusion and exclusion criteria section) will ensure subjects meet all inclusion criteria. They will be subsequently randomized to one of three study groups according to a computer-generated randomization number table.

II. Study Medication Administration Protocol

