Ketamine + Methadone	Preinduction: 0.2 mg/kg methadone IV bolus Induction: ketamine 0.5 mg/kg IV bolus Infusion: ketamine 5 mcg/kg/min IV

III. Preoperative Evaluation (on the day of surgery):

- In the preoperative holding area, patients will provide a detailed medical history, including demographic information (e.g., age, weight, height, ethnic origin, smoking history, anesthetic complications such as postoperative nausea and vomiting, baseline VRS pain scores, and current pain medication regimen. An anesthesiologist will perform

the physical exam and written informed consent will be obtained by one of the investigators.

b. Enrollment numbers: A total of 114 patients, aged 18-80 years, American Society of Anesthesiology (ASA) physical status I – III undergoing lumbar laminectomy will be randomly assigned to one of three study groups:

Group I	Ketamine (n = 38)
Group II	Methadone (n = 38)
Group III	Ketamine & Methadone (n= 38)

IV. Intraoperative period:

- a. Premedication: Midazolam 20 ug/kg IV for anxiolysis, amnesia, and sedation synergism.
- b. Standard monitors: automatic blood pressure cuff, non-invasive blood pressure three-lead electrocardiogram, capnograph, pulse oximeter, urinary temperature monitor and bispectral index (BIS) monitor will be used. Patient will be pre-oxygenated with a simple face mask at 6 L/min for at least 2 minutes.
- c. Anesthesia induction technique: Fentanyl 50-100 mcg IV, propofol 1.5-3 mg/kg IV with lidocaine 1-1.5 mg/kg IV will be given for induction. Choice of muscle relaxant for intubation will be left up to the discretion of the anesthesiologist. Both histamine release from succinylcholine and the mild vagal blockade of rocuronium are negligible and are not known to interfere with pain control.
- d. Normothermia will be maintained with forced-air warming and IV fluid warmers.
- e. Administration of study medication will occur as follows:

Group	Dosing (IBW used for mg/kg dosing)
I – Ketamine	Preinduction: Sham (0.9% normal saline, volume calculated to match methadone dose) Induction: 0.5 mg/kg IV bolus Infusion: 5 mcg/kg/min IV
II – Methadone	Preinduction: 0.2 mg/kg IV bolus Induction: Sham (0.9% normal saline, volume calculated to match ketamine induction dose) Infusion: Sham (0.9% normal saline at infusion rate calculated and adjusted for weight to match ketamine bolus-infusion rate)

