- I. Preoperative demographics: age, weight, BMI, gender, ASA status, race, preoperative medications including beta-blockers and Lidoderm patches, prior back surgery, prior pain procedures, past medical/surgical history, social history (smoking, drinking, illicit drug use) allergies, history of postoperative nausea and vomiting, history of motion sickness and short-form 12 (SF-12) score after completing the survey. Name, phone number, e-mail address, and medical record number will be collected and stored in a secured separate file to prevent bias and inadvertent unblinding. Only the study coordinator will have access to this file and the patient will be referred to solely by subject number.
- II. Preoperative data: baseline VRS pain score, vital signs (blood pressure, heart rate, temperature, respiratory rate, oxygen saturation via pulse oximetry), 12-lead EKG interpretation, duration of pain, any abnormal lab results, additional surgical procedures (e.g., fusion, discectomy), and number of levels.
- III. Intraoperative data:
 - Vital signs (including blood pressure, heart rate), BIS values, every 5 – 10 minute intervals
 - dosages of all medications given (anesthetics, analgesics, local anesthetics, rescue medications, adjuncts such as decadron, end-tidal desflurane concentration, rate of propofol infusion), IV fluids, blood products, colloids, blood loss, urine output
 - Duration of surgery (from skin incision to closure), duration of anesthesia (from IV induction until anesthetic drug discontinuation)

IV. Postoperative data:

- Time on arrival to PACU, departure, and total length of stay
- VRS pain score and nausea on arrival to the PACU, vital signs, opiate and antiemetic requirements in the PACU
- PACU complications such as respiration depression (respiratory rate < 8, need for naloxone, or respiratory arrest), hypoxemia or desaturation ($\text{SpO}_2 < 90\%$ or need of supplemental oxygen to maintain $\text{SpO}_2 > 95\%$), hypotension, cardiac arrhythmias, myocardial infarction, nausea and vomiting, respiratory distress.
- Total opioid, adjuvant (e.g., anticonvulsants, antispasmodics, SSRI's) and antiemetic consumption at 24, 48, and 72 hours following surgery. If patients are discharged from the hospital prior to 72 hours, a telephone interview will be conducted to determine opioid/adjuvant consumption at home.

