- VRS pain scores, vital signs and medication side effects (e.g., ketamine-induced hallucinations) at 24, 48, and 72 hours following surgery; time to return of daily activities (oral diet, return of bowel function, ambulation, showering) in days, any complications such as cardiac arrhythmias, global evaluation of anesthesia experience with 0 = worst, 10 = best
- Length of hospital stay

V. 6 week post-surgical assessment data:

- VRS pain score, opioid/adjuvant consumption, medication side effects (e.g., hallucinations, constipation, nausea and vomiting), SF-12 score.

Note: all opioid consumption will be converted to morphine equivalents for data analysis and presentation.

DATA ANALYSIS

Sample size estimates were based on the test for inequality of opioid consumption among the methadone, ketamine, and ketamine + methadone groups. We expect to observe at least a 30% decrease in opiate consumption between ketamine + methadone group and methadone or ketamine. Prior studies demonstrated that the postoperative opioid consumption and its standard deviation for methadone and ketamine are quite similar (10, 21). Mean opioid consumption was approximately 67 mg \pm 38 mg (SD) for Menigaux's et al. ketamine group and median 63 mg (interquartile range, 27-86.1), which gives an estimated SD of 23. The expected group mean difference would be 18.9 for an approximate 30% decrease in opioid requirements. However, we would like to be more conservative in our study since the aforementioned study populations were most likely skewed. For a two-tailed hypothesis with alpha 0.05, we would need at least 38 subjects per group to achieve a power of 0.8 to detect a 30% reduction in opioid consumption.

Two group t-test of equal means (equal n's)

	1	2	3	4
Test significance level, α	0.050	0.050	0.050	0.050
1 or 2 sided test?	2	2	2	2
Group 1 mean, μ_1				
Group 2 mean, μ_2				
Difference in means, $\mu_1 - \mu_2$	18.900	20.000	17.000	15.000
Common standard deviation, σ	23.000	23.000	23.000	23.000
Effect size, $\delta = \mu_1 - \mu_2 / \sigma$	0.822	0.870	0.739	0.652
Power (%)	80	80	80	80
n per group	25	22	30	38

Similarly for VAS pain scores, previous studies found average scores to range from 2.8 ± 2.0 for methadone group and 5.4 ± 2.0 for the ketamine study (7, 10). With alpha 0.05, power 0.8 and mean difference of 1.6, each group needs at least 17 subjects to observe a 30% reduction in VAS pain scores.

Two group t-test of equal means (equal n's)

	1	2	3	4

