If the postoperative EKG demonstrates prolonged qTc interval of >470 ms for men and >480 ms for women OR a 60 millisecond (or 25%) increase from baseline, the patient will be placed on telemetry. Serum potassium and magnesium levels will be monitored closely and replaced as necessary. If the patient enters Torsades de Pointes and is hemodynamically unstable, prompt nonsynchronized electric defibrillation can be performed. A magnesium sulfate infusion will be started for treatment and prevention. If the patient does not respond to magnesium, transvenous overdrive pacing at 100 beats per minute will be instituted. Isoproterenol (starting at 2 mcg/min and titrating to heart rate of 100 beats per minute) can also be used as a temporizing measure while transvenous pacing is being setup.

The patient will be admitted to the critical care unit if they have hemodynamic instability, syncope, or ventricular ectopy, T wave alternans, AV block or QRS widening on their postoperative EKG.

In general, less likely and rare side effects are seen in higher than clinically acceptable doses or prolonged use of the drug. Those with co-existing diseases that increase the likelihood of the more rare and severe side effects such as increased intracranial pressure will be excluded. Ketamine has an elimination half-life of 3-5 hours while methadone's elimination half-life ranges from 24 – 36 hours (22). On average, lumbar laminectomy duration has been 2-3 hours. An additional 1-3 hours is spent in the PACU. Nausea and vomiting will be treated with an antinauseant such as ondansetron IV.

MANTAINANCE OF CONFIDENTIALITY

Patients' names will not be divulged and all data will be coded in the study records in accordance with standard HIPPA policy. Information gained during the course of the study will only be used by the investigators for the purpose of evaluating the effects of ketamine infusion with methadone during the intraoperative and postoperative period. All data will be coded in the study records. Copies of signed informed consent will be kept on file by the principal investigator, and no patient names or other identifying information will be used in any future publications.

SPECIAL PRECAUTIONS

All drugs will be used by an anesthesiologist who is familiar with them and trained to handle any untoward events related to medications

RISK-BENEFIT ASSESSMENT

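### No prompted check for hallucinations, dysphoria, confusion or sedation in the PACU, and no recall window for the 24-hour question, so Objective 2 may under-record transient ketamine effects

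*Combined protocol and SAP*

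**What the plan says.** The second of the STUDY OBJECTIVES is "To compare the side effects and hospital course between post-laminectomy patients receiving intraoperative ketamine + methadone vs. ketamine or methadone alone". DATA ANALYSIS assigns side effects to a chi-squared or Fisher's exact test.

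Ketamine is given as a bolus at induction and then by infusion, which ends at skin closure (METHODS, VI). POTENTIAL RISKS states "Ketamine has an elimination half-life of 3-5 hours" and puts the PACU stay at 1-3 hours.

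PATIENT DATA COLLECTION, IV, has three relevant items:

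- On PACU arrival: "VRS pain score and nausea on arrival to the PACU, vital signs, opiate and antiemetic requirements in the PACU".
- In the PACU: "PACU complications such as respiration depression (respiratory rate < 8, need for naloxone, or respiratory arrest", followed by low oxygen saturation, hypotension, arrhythmia, myocardial infarction, nausea and vomiting, and respiratory distress.
- Later: "VRS pain scores, vital signs and medication side effects (e.g., ketamine-induced hallucinations) at 24, 48, and 72 hours following surgery".

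Section V of the same part adds a 6-week assessment: "VRS pain score, opioid/adjuvant consumption, medication side effects (e.g., hallucinations, constipation, nausea and vomiting), SF-12 score". SUMMARY OF STUDY DESIGN agrees with this calendar: "Opiate consumption, VRS pain scores, and adverse events will be recorded on post-operative days one to three and at six weeks".

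Premedication (METHODS, IV, item a) is "Midazolam 20 ug/kg IV for anxiolysis, amnesia, and sedation synergism".

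**The concern.** RISK-BENEFIT ASSESSMENT describes the side effects of analgesic doses as transient. The plan nevertheless schedules the first assessment that names ketamine's characteristic effect a day after the drug is stopped, and no PACU item prompts for it. Nausea is prompted on arrival, so the plan does name patient-reported symptoms in the PACU when it wants them.

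At stake is the reading of Objective 2. If brief episodes around emergence are recorded only when someone volunteers or remembers them, similar rates across arms could come from the timing of the question as well as from the drugs. The exposed contrast is combination versus methadone alone, because only one of those arms receives ketamine.

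**Working it through.** The plan gives no figure of its own on this point to reproduce. The check uses its half-lives and schedule.

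**Inputs.** Ketamine half-life h = 3 to 5 h, methadone half-life 24 to 36 h, PACU stay 1 to 3 h and operation 2 to 3 h (all POTENTIAL RISKS); infusion stopped at skin closure (METHODS, VI); first assessment naming hallucinations at 24 h after surgery (PATIENT DATA COLLECTION, IV); 38 patients per group (DATA ANALYSIS). Because the infusion ends at closure, 24 h after surgery is about 24 h after the infusion.

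**Ketamine remaining.** Assuming first-order elimination, half-lives elapsed = t/h and fraction remaining = 2^(-t/h).

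| Time after infusion | h = 3 h | h = 5 h |
|---|---|---|
| 1 h | 0.33 half-lives, 79% | 0.2 half-lives, 87% |
| 3 h | 1.0 half-lives, 50% | 0.6 half-lives, 66% |
| 24 h | 8.0 half-lives, 0.4% | 4.8 half-lives, 3.6% |

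These figures describe exposure. They are not counts of symptoms.

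**Contrast with methadone.** The dose is given before induction, so 24 h after a 2-3 h operation is about 26-27 h after the dose. That is 26/36 = 0.7 to 27/24 = 1.1 half-lives. The 24 h contact therefore falls while methadone is still present and ketamine largely is not.

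**What under-recording could do (illustration only).** POTENTIAL RISKS cites central nervous system side effects in 9% of ketamine patients after a single IV dose and 10% with IV infusion. Per 38-patient arm that is 38 × 0.09 = 3.4 or 38 × 0.10 = 3.8 events. The share that a 24 h question would capture is unknown. At 10% incidence and assumed capture of 100%, 50% or 25%, the expected recorded counts are 3.8, 3.8 × 0.5 = 1.9, or 3.8 × 0.25 = 1.0.

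Two cautions apply. The cited percentages cover dizziness and drowsiness as well as hallucinations, dysphoria and confusion. They are also totals, not excess over a comparator: the pooled comparison in the same section is 18% with postoperative ketamine plus morphine against 15% with morphine alone (P = 0.31).

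**What the text leaves open.** No recall window is given for the 24 h side-effect item, no instrument is named for hallucinations, and no passage gives the timing of such events.

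**The case against.** The strongest reply is that the 24 h item may be an interval question. The neighbouring item on total opioid consumption uses the same three times and must be cumulative, and the design summary's wording about days one to three also fits an interval record. On that reading emergence is covered. This stands as a possible reading, but the plan does not state it. Recall would also be asked of patients premedicated partly for amnesia, although no passage says how long that amnesia lasts.

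Second, the PACU list is introduced as examples, so a hallucination could be entered. A further item asks for any complications, investigators may see medical records (DATA HANDLING/RESOURCING), and PACU discharge requires an alert patient without intractable side effects. The period is therefore not unobserved. But none of these is a prompted data item, and the discharge rule would not record a brief or tolerable episode.

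Third, the combination and ketamine-alone arms have the same planned ketamine regimen, so under-recording should affect both similarly. That stands, and it narrows the point mainly to combination versus methadone.

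Fourth, better timing would not make that contrast decisive. With 4/38 against 0/38, the two-sided Fisher p is 2 × C(38,4)/C(76,4) = 2 × 73,815/1,282,975 = 0.115. That also stands: the gain is in valid recording, not in power.

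A reader might go further and infer that the trial will miss most of these effects, that they cannot be present at 24 h, or that all arms will show rates near zero. The documents do not support this. The question may look back, the PACU list is open, event timing is not given, and methadone and postoperative opioids can produce confusion or drowsiness at 24 h in any arm.

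**Conclusion.** The point holds as a gap in prompted measurement. Hallucinations, dysphoria, confusion and sedation are not solicited during emergence or the PACU stay, when 50-87% of the end-of-infusion ketamine level remains. The first assessment naming hallucinations comes at 4.8-8.0 half-lives with an undefined recall window. Objective 2 may therefore under-record transient ketamine effects, chiefly in combination versus methadone alone, and a finding of no difference could partly reflect assessment timing.

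The size of the loss cannot be computed from the documents. The conclusion rests on the plan's half-life, on first-order elimination, and on the inference that transient effects are likelier while more drug is present. It concerns a secondary objective and is a cheap improvement: the added items would improve capture whether or not the 24 h question was meant to look back.

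**What to change.** In PATIENT DATA COLLECTION, IV, add hallucinations, dysphoria, confusion and sedation to the PACU data as solicited yes/no items. Have the blinded data collector ask them at the two PACU contacts where METHODS, VI, already requires a pain score: on arrival and before discharge. In the 24 h item, state that the side-effect question covers the whole period since the end of surgery. The 48 h, 72 h and 6-week assessments can stay as they are.

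The cost is a few tick-boxes at existing contacts, with no new visit and no change to treatment. Some drowsy patients will not be ratable on arrival. Record them as not assessable, not as free of symptoms, and rely on the pre-discharge check for those items.

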Test significance level, α	0.050	0.025	0.050	0.025
1 or 2 sided test?	2	2	2	2
Group 1 mean, μ_1				
Group 2 mean, μ_2				
Difference in means, $\mu_1 - \mu_2$	2.000	2.000	1.800	1.800
Common standard deviation, σ	2.000	2.000	2.000	2.000
Effect size, $\delta = \mu_1 - \mu_2 / \sigma$	1.000	1.000	0.900	0.900
Power (%)	80	80	80	80
n per group	17	21	21	25

Based on the power analysis, a sample size of 38 patients for each group will sufficiently allow us to detect at least a 30% reduction in postoperative opioid consumption and VAS pain scores with 80% power using a two sample t-test, significance level of 0.05 (two-sided). Total sample size will be 114.

ANOVA will be used to compare the continuous variables among the three treatment groups, and when significant differences are determined, a Newman-Keuls multiple-comparison test will be used to determine intergroup differences. Continuous data not normally distributed are analyzed by Kruskal-Wallis test, and when a significant difference is found, a Mann-Whitney U test is used for post-hoc comparisons between the intergroups. Chi-squared test (or Fisher's exact test) is used to analyze the categorical variables such as side effects and sex distribution.

INCLUSION & EXCLUSION CRITERIA

I. Inclusion criteria:

- 18 – 80 years old of either gender, scheduled for elective lumbar laminectomy

II. Exclusion criteria:

- ASA IV and above
- Intolerance, allergy, or contraindication to use of any medications used in this study
- Significant coronary artery disease (abnormal stress test, myocardial infarction within the last 3 months)
- Increased intraocular pressure (e.g., untreated glaucoma)
- Uncontrolled hypertension (BP > 140/90)
- Sleep apnea AND currently on continuous positive airway pressure (CPAP)
- Increased intracranial pressure or clinical signs thereof
- History of intracranial surgery, stroke, or brain aneurysm
- Cardiac arrhythmias particularly prolonged QT syndrome
- Drugs known to cause prolonged QT: class IA antiarrhythmics (quinidine, procainamide, dysopyramide), class III antiarrhythmics (sotalol, dofetilide, ibutilide, amiodarone), haloperidol, thioridazine, arsenic trioxide, HIV protease inhibitors, tricyclic antidepressants
- Individuals with significant psychological disorders including: schizophrenia, mania, bipolar disorder or psychosis
- Pregnant or lactating women
- Emergent laminectomy
- Those already receiving ketamine or methadone prior to surgery

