- Morbid obesity (BMI > 40 kg/m²) AND/OR weight \geq 150 kg
- Chronic renal failure (creatinine > 2.0 mg/dL)
- Liver failure e.g., active cirrhosis
- Alcohol or substance abuse within in the past 3 months
- Uncorrected hypokalemia, hypomagnesemia, hypocalcemia (can be due to diuretics, mineralocorticoid use, laxatives)
- COPD/Hypercarbia
- Restrictive lung disease (pulmonary fibrosis, myasthenia gravis)
- Congestive heart failure
- Thyroid disease
- Organ transplant patients
- Drugs/substances known to inhibit methadone metabolism: macrolide antibiotics e.g., erythromycin, cimetidine, astemizole, voriconazole, grapefruit juice

DATA HANDLING/RESOURCING

Investigators will have access to the patients' medical records and the results of all examinations undertaken as part of this clinical trial. All data will be recorded in forms provided by the investigators. Collected data will be coded and used for research purposes only.

SUBJECT RECRUITMENT

Study investigators will contact surgeons and present this study protocol to them. Prior to surgery, (ideally during patients preoperative appointments) the surgeon will inform the patient of this study and obtain a consent for contact letter signed by the interested patient. The patient will also be provided with an informed consent form. Study staff will follow-up with the surgeon's office (or vice-versa) and conduct a phone interview with the patient to determine eligibility. Patients who intend on participating in the study will sign the informed consent form and the investigator will record that the subject has had completed their informed consent well before the scheduled procedure. Risk and benefits will be reviewed with the subject. They reserve the right to voluntarily exit the study at any time without any penalty. Patients will be explained that general anesthesia will be used during the study.

POTENTIAL RISKS

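### Time to return of daily activities has no stated end of follow-up and no censoring rule, so late recoveries may go undated and arm differences may be attenuated

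*Combined protocol and SAP*

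**What the plan says.** All references are to the combined protocol and SAP.

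- **Patient Data Collection, IV. Postoperative data** lists "time to return of daily activities (oral diet, return of bowel function, ambulation, showering) in days". It gives no time origin, no definition of each event and no last day of observation. The item follows a semicolon after "VRS pain scores, vital signs and medication side effects (e.g., ketamine-induced hallucinations) at 24, 48, and 72 hours following surgery".
- The same section provides a contact for patients who leave hospital before 72 h, with a stated purpose: "a telephone interview will be conducted to determine opioid/adjuvant consumption at home".
- **V. 6 week post-surgical assessment data** is a closed list: "VRS pain score, opioid/adjuvant consumption, medication side effects (e.g., hallucinations, constipation, nausea and vomiting), SF-12 score". Constipation appears as a side effect, but no date of return of any activity is requested.
- **Summary of Study Design** gives the recording schedule: "Opiate consumption, VRS pain scores, and adverse events will be recorded on post-operative days one to three and at six weeks". Activities are not named.
- **Data Handling/Resourcing** states: "Investigators will have access to the patients' medical records".
- **Data Analysis** states: "ANOVA will be used to compare the continuous variables among the three treatment groups". It adds: "Continuous data not normally distributed are analyzed by Kruskal-Wallis test". It contains no time-to-event method, no censoring rule and no rule for missing values.

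**The concern.** A time to an event needs an end of observation and a rule for patients who have not had the event by then. Neither is given. Of the contacts listed, none is stated to date a bowel movement or a shower that happens at home. The gap can open before 72 h: a patient discharged on day 1 or 2 is telephoned, but the call is described only for medication use.

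Whether a value is missing would then depend on the value itself, because late events are the ones not seen. The arm with more late events loses more of its long times and looks closer to the others than it is. An arm difference in bowel function is plausible. The Potential Risks table lists constipation under methadone, the Background says methadone constipates less than other opioids, and every patient receives some narcotic after the PACU. The direction of any difference is therefore not obvious in advance.

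At stake is a recovery measure that serves the title's reference to recovery and the second objective's comparison of hospital course.

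**Working it through.** **1. The plan's own figure.** The documents give no expected recovery time and no sample size for this endpoint. The 38 per group comes from opioid consumption: 2 × (1.960 + 0.842)² × 23² / 15² = 36.9 by the normal approximation, and 37.9 by the exact t-test, so 38. It reproduces, but serves here only as the arm size.

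**2. Which listed contact would date an event?**

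| When the event occurs | Stated source |
|---|---|
| In hospital, by 72 h | Assessments at 24, 48 and 72 h; chart |
| In hospital, after 72 h | Chart access only |
| At home, by 72 h | Telephone call, stated for opioid/adjuvant use only |
| At home, after 72 h | 6-week contact, which omits the item |

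**3. Effect on the mean difference (assumed inputs).** Let times be lognormal with median m and log-SD s, and let the cut-off be c = 3 days. Put z = (ln c − ln m)/s.

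- Share beyond c: 1 − Φ(z)
- True mean: M = m·exp(s²/2)
- Mean if late values are deleted: M·Φ(z − s)/Φ(z)
- Mean if late values are set to c: M·Φ(z − s) + c·(1 − Φ(z))

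Example with s = 0.4 and medians 2.0 and 2.75:

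- Faster arm: z = 0.405/0.4 = 1.014, share beyond 3 days 15.5%, M = 2.167. Deleted: 2.167 × 0.730/0.845 = 1.873. Capped: 2.049.
- Slower arm: z = 0.087/0.4 = 0.218, share 41.4%, M = 2.979. Deleted: 2.979 × 0.428/0.586 = 2.173. Capped: 2.516.
- True difference 2.979 − 2.167 = 0.81. Deleted: 0.30, a loss of 1 − 0.300/0.812 = 63%. Capped: 0.47, a loss of 42%.

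| s | Medians (days) | Share > 3 days | True diff. | Deleted (loss) | Capped (loss) |
|---|---|---|---|---|---|
| 0.4 | 1.0 / 1.35 | 0.3% / 2.3% | 0.38 | 0.34 (11%) | 0.37 (3%) |
| 0.5 | 1.0 / 1.35 | 1.4% / 5.5% | 0.40 | 0.30 (24%) | 0.36 (9%) |
| 0.4 | 2.0 / 2.75 | 16% / 41% | 0.81 | 0.30 (63%) | 0.47 (42%) |
| 0.4 | 2.5 / 3.25 | 32% / 58% | 0.81 | 0.20 (75%) | 0.32 (61%) |
| 0.4 | 3.0 / 3.75 | 50% / 71% | 0.81 | 0.14 (83%) | 0.20 (75%) |
| 0.5 | 2.0 / 2.75 | 21% / 43% | 0.85 | 0.26 (70%) | 0.42 (51%) |
| 0.5 | 2.5 / 3.25 | 36% / 56% | 0.85 | 0.18 (79%) | 0.29 (66%) |
| 0.5 | 3.0 / 3.75 | 50% / 67% | 0.85 | 0.13 (84%) | 0.20 (77%) |

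**4. Effect on power (assumed inputs).** This is a simulation with 38 per arm, whole-day times, log-SD 0.5, a 30% shorter median in the combination arm, 1,500 replicates and a two-sided 5% test.

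| Single-drug median (days) | Mann-Whitney, all times known | Mann-Whitney, > 3 days deleted | Log-rank, censored at day 3 |
|---|---|---|---|
| 0.71 | 51% | 51% | 53% |
| 1.43 | 81% | 71% | 80% |
| 2.14 | 80% | 48% | 78% |
| 2.86 | 82% | 30% | 78% |
| 4.29 | 83% | 9% | 70% |

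Under deletion, power falls as more patients pass day 3. Censoring at day 3 keeps most of it without any later data.

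**The case against.** The strongest reply is that the protocol never says collection stops at 72 h. The 24, 48 and 72 h times attach to pain scores, vital signs and side effects. The activities item comes after the semicolon with no limit, as does length of stay in the next bullet. Chart access is not limited to 72 h either, and a 6-week contact exists. A reader might infer that there is no contact after 72 h and that slow recoverers drop out of the analysis. The documents support neither statement: the 72 h limit is an inference, and no text says late cases are excluded. What stands is narrower. No listed contact is stated to date an event that happens at home, and no rule covers a patient whose event has not been seen.

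The second reply is that the large losses depend on deletion and on medians placed near the cut-off. That is fair. Under capping, a rank test loses little: with log-SD 0.4, Mann-Whitney power at 38 per arm goes from 91% to 90% at medians 2.0/2.75 and from 65% to about 52% at 3.0/3.75, whereas deletion leaves at most about 50% in any of the scenarios with medians of 2 days or more. With medians near 1 day, which may suit diet or walking better than bowel function or showering, the absolute loss is at most 0.10 day. No single percentage can be offered as the trial's expected loss.

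The third reply is that the hypotheses and the sample size concern pain and opioid use only. This also stands, and it limits the priority.

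**Conclusion.** The gap is real but minor. The plan collects a time endpoint without an end of follow-up, without a stated contact for events after discharge, and without censoring. If late cases are left out or set to the last assessed day, arm differences in this secondary recovery measure are attenuated.

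The amount cannot be known from the documents. Under the lognormal assumptions above it runs from no visible change (single-drug median 0.71 days) through 0.04 to 0.10 day (medians 1.0/1.35) to about 63% to 84% of the mean difference (medians 2 to 3.75 days) if values over 3 days are deleted. If they are capped at 3 days the loss is 42% to 77% of the mean difference over the same medians, and smaller for a rank test. These figures rest on an assumed common shape in both arms and an assumed 3-day cut-off. The conclusions on pain scores and opioid consumption are not affected.

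**What to change.** - Define each of the four events and a common time origin, for example the end of surgery.
- Add the date of each event to the existing telephone interview, and to the 6-week form for anyone who had not reached it by then.
- Replace ANOVA/Kruskal-Wallis on observed days, for these items only, by Kaplan-Meier curves and a log-rank test with censoring at last contact. Censoring everyone at 72 h, or comparing the proportion recovered by 72 h, would also do. Choose one in advance.
- Do not censor at discharge. Readiness to leave hospital is likely to be related to recovery, so such censoring would be informative. The telephone question is what makes a fixed 72 h cut-off workable.

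The cost is four questions at contacts that already exist and a sentence or two in Data Analysis. The downside is that dates recalled at 6 weeks are imprecise. An analysis censored at 72 h does not need them, at the price of some power if many patients recover later (for example 70% against 83% at a single-drug median of 4.29 days).
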